8.2 Plan modification

8.3 Informed consent

8.4 Confidentiality

1. ABSTRACT

Basic information on clinical practice of medical devices:

Device Classification: Class II medical devices

Specification Model: RS-200-1A

Date: September 20, 2020

Sponsor: Zuoguan Medical Devices Co., Ltd. at Suzhou Industrial Park

Practice Title

A Randomized, Controlled, Multi-centre Clinical Study on the Effectiveness and Safety of repeated low-level red-light (RLRL) for myopia control in children and adolescents with high myopia

Practice Purpose

A Study on assessing the effectiveness and safety of RLRL for myopia control in children and adolescents with high myopia.

Subject Population

Subject: Children aged 6-16 with at least one eye with myopia of cycloplegic spherical equivalent refraction (SER) at least -4.0 D

Sample size: 192 subjects are planned to be enrolled and assigned to the intervention group or control group according to a ratio of 1:1

Practice Design

Overall design:

This prospective, single-blind, parallel-group, multi-center randomized clinical trial was conducted at six tertiary hospitals. Participants between 6 and 16 years old with at least one eye with a spherical equivalent refraction (SER) of -4.0 D or greater were recruited. The enrolled participants were randomly placed at a 1:1 ratio into

intervention (RLRL treatment plus single-vision spectacles) or control (single-vision spectacles) groups. The participants attended follow-up appointments 1, 3, 6, 9, and 12 months after the baseline evaluation.

Outcomes:

1. Primary Outcome: Change of Axial length (AL, mm) at 12-month follow-up
2. Secondary Outcome: Change of cycloplegic spherical equivalent (SE, D) at 12-month follow-up
3. Optional Indicators:

Changes of uncorrected visual acuity (UCVA), best-corrected visual acuity (BCVA), intraocular pressure, etc.;

Changes of corneal thickness (CT), anterior chamber depth (ACD) and lens thickness (LT);

Observe macula and the structure of fundus around the optic disc;

Observe the choroid/retinal thickness of the fundus;

Compliance index: frequency of equipment uses.

Safety assessment

- ① Sudden vision loss;
- ② Afterimage time over 5 minutes;
- ③ Side effects such as glare, photophobia and flickering;
- ④ Structural damage to retina: tissue disruption or discontinuity, edema, or other abnormalities in the photosensory layer of the SS-OCT images;
- ⑤ Increased intraocular pressure etc.

Participants selection and exclusion criteria:

Eligibility criteria:

Inclusion criteria:

- ① Age 6-16 years old, no gender limit;
- ② Either eye meets the diagnosis of myopic refractive error and the myopia of cycloplegic spherical equivalent refraction (SER) at least -4.0 D, astigmatism 2.0 D

or less, anisometropia 3.0 D or less, and best-corrected visual acuity (BCVA) of LogMAR 0.2 or better.

- ③ Have normal thinking and language communication skills, and be able to actively cooperate with the required treatment;
- ④ No contraindications to the treatment of atropine such as acute ocular inflammation, dry eye, keratoconus, diabetes, etc.;
- ⑤ Written informed consent of the guardian and the child.

Exclusion criteria:

1. History of photosensitivity, glaucoma, glaucoma syndrome, ocular hypertension, and macular pathology or damage in the fundus;
2. The average K value of the anterior surface of the cornea is ≥ 45 in corneal curvature examination;
3. Patients with systemic diseases such as heart, liver, kidney, and congenital hereditary myopia;
4. Patients with chronic eye diseases such as eye trauma and strabismus or surgical eye, atopic keratoconjunctivitis;
5. People who have had other eye diseases such as inverted trichiasis, severe corneal and conjunctival infections in the past;
6. People with neurological diseases and allergies or contraindications to atropine drugs or other therapeutic drugs;
7. Patients with immune system and systemic diseases such as albinism, psoriasis, nephrotic syndrome, systemic lupus erythematosus, diabetes, etc.;
8. People with epilepsy and mental disorders who cannot communicate normally;
9. Individuals who have previously received other treatments to control the development of myopia, such as the use of anticholinergic drugs such as atropine within 3 months, or participated in other related researches such as functional frame mirrors, multifocal soft mirrors, etc.;
10. Other situations that the researcher judges are not suitable for participating in the study.

Control type:

Comparison of the effect of routine single vision spectacle lenses

Statistical analysis plan:

The intention-to-treat (ITT) population comprised participants randomly assigned to either group. Data from all participants who attended at least one subsequent follow-up visit were included in the analysis. Individuals who switched to other myopia treatment modalities or discontinued the RLRL treatment, were censored.

Treatment efficacy was assessed using longitudinal mixed models for primary (changes in AL) and secondary (changes in SER and IOP) outcomes at multiple follow-up visits. Sensitivity analyses were conducted to assess the treatment effects of therapy in controlling myopia progression, specifically axial elongation and SER progression, across different baseline SER and age groups.

A longitudinal mixed-model analysis was conducted to assess the relationship between treatment efficacy and compliance within the intervention group.

Safety analyses were performed in the ITT population. All adverse events were reported individually.

Ethics:

The practice protocol (including the informed consent form) is submitted to the ethics committee for approval, and all subjects entering the trial screening must sign the informed consent form. Researchers should conduct experiments in strict accordance with the experimental protocol and GCP requirements to fully protect the legal rights and safety of the subjects.

2.3 Study Purpose

Study on effectiveness and safety of repeated low-level red-light in controlling high myopia in children and adolescents.

2.4 Research Background

Myopia, or nearsightedness, is a prevalent refractive error of the eye characterized by the ability to see close objects clearly while distant objects appear blurred. High myopia, defined as a refractive error of -6.00 diopters or more, poses a significant public health concern due to its increasing prevalence, particularly among children and adolescents worldwide^[1-4]. High myopia not only impairs visual acuity but also substantially raises the risk of sight-threatening complications such as myopic macular degeneration,

glaucoma or even retinal detachment^[5].

Despite the growing prevalence and potential vision-threatening consequences of high myopia, effective strategies for its control and management remain elusive. High myopia is often out of range as an indication for orthokeratology^[6]. Low-concentration atropine^[7-10] or defocus spectacles^[11] have demonstrated reasonable efficacy on controlling low or moderate myopia in multiple randomized controlled trials (RCTs) but no evidence suggests their efficacy among highly myopic eyes.

The Eyerising amblyopia treatment instrument has been widely used in mainland China to treat amblyopia. The instrument utilizes repeated low-level red-light (RLRL) for treatment. Some studies confirm that it can improve the vision of patients, and no local or systemic side effects have been found^[12]. Low-intensity lasers can cause photochemical reactions in the retina, including increasing the activity of cytochrome C oxidase^[13,14] changing gene expression to regulate the mitochondrial respiratory chain^[15], and increasing the biological activity of nitric oxide^[16]. Preliminary trial data shows that it has a significant effect on slowing down the progression of myopia. This study will explore the effect of RLRL therapy in the prevention and treatment of high myopia for the first time. If successful, it will provide new ideas for effectively controlling myopia.

3. STUDY DESIGN

This trial is a randomized, controlled, multi-centre clinical trial. The subjects selected 192 children aged 6-16 who had developed high myopia, and divided them into intervention group and control group with 96 cases each. The intervention group was treated with the Eyerising RLRL and single vision spectacle lenses, and the control group was treated with single vision spectacle lenses. Then, we compare the changes of myopia during the observation period between the two groups, and evaluate the safety and effectiveness of the test device.

Subjects will be screened after signing the informed consent form (as early as 7 days before the randomization day). The screening test can use the results of the ophthalmological examination in hospital within 1 week, and subjects enter the group after confirming that they meet the selection conditions. On the day of enrolment, the group is confirmed after consultation with the parents, and determine whether to receive

equipment for treatment based on the results of the grouping. Visits were conducted 30±14 days, 90±14 days, 180±14 days, 270±14 days, and 365±14 days after enrolment.

3.1 Eligibility criteria

Inclusion criteria

- ① Age 6-16 years old, no gender limit;
- ② Either eye meets the diagnosis of myopic refractive error and the myopia of cycloplegic spherical equivalent refraction (SER) at least -4.0 D, astigmatism 2.0 D or less, anisometropia 3.0 D or less, and best-corrected visual acuity (BCVA) of LogMAR 0.2 or better.
- ③ Have normal thinking and language communication skills, and be able to actively cooperate with the required treatment;
- ④ No contraindications to the treatment of atropine such as acute ocular inflammation, dry eye, keratoconus, diabetes, etc.;
- ⑤ Written informed consent of the guardian and the child.

Exclusion criteria

- ① A history of photosensitivity, glaucoma, glaucoma syndrome, ocular hypertension, and macular pathology or damage in the fundus;
- ② Corneal curvature examination, the average K value of the anterior surface of the cornea is ≥ 45 ;
- ③ Patients with heart, liver, kidney and other systemic diseases and congenital hereditary myopia;
- ④ Patients with chronic eye diseases such as ocular trauma and oblique or surgical eyes, atopic keratoconjunctivitis;
- ⑤ Patients with previous eye diseases such as inverted trichiasis, severe corneal and conjunctival infections;
- ⑥ Patients with neurological diseases and allergies or contraindications to atropine drugs or other therapeutic drugs;
- ⑦ Patients with immune system and systemic diseases such as albinism, psoriasis, nephrotic syndrome, systemic lupus erythematosus, diabetes, etc.;
- ⑧ People with epilepsy, mental disorders and unable to communicate normally;

- ⑨ Those who have previously received other treatments to control the development of myopia, such as the use of anticholinergic drugs such as atropine within 3 months, or participated in other functional frame mirrors, multifocal soft mirrors and other related researchers;
- ⑩ Other situations that the researcher judges are not suitable for participating in the research.

Participant withdrawal or termination

A study investigator will terminate participation in the study for the following reasons:

- 1) The patient receives other myopia control treatments;
- 2) Patients continuously stop using Eyerising equipment for more than 14 days;
- 3) Severe comorbidities or adverse events: patients cannot tolerate light, have obvious eye allergies such as tearing, skin rash, and the after-image time after low-energy laser treatment exceeds 5 minutes;
- 4) Serious safety problems occurred repeatedly during the test (such as serious adverse events related to the test);
- 5) China Food and Drug Administration ordered the suspension of the test for some reason;
- 6) Sponsor requests suspension (such as funding reasons, management reasons, etc.).

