7) Slit-lamp examination: Slit-lamp examination will be used to examine the anterior segment, lens, vitreous, and fundus, and any abnormalities will be recorded.

8) Optical coherence tomography (optional): SS-OCT fundus image acquisition and data processing: using swept source OCT (DRI OCT-1 Atlantis, Topcon) 9 Line Radial follow-up mode to scan and collect images to obtain fundus pictures and fundus tissue tomographic images. Before the collection, the subjects should be asked to sit still for a while, avoid taking coffee and drinks; during collection, doctors should pay attention to correct the axial magnification; researchers should concentrate on collection time to avoid the influence of the time rhythm fluctuation of choroidal thickness. After the choroidal boundary is automatically segmented by the machine's built-in software,

manual verification and correction are carried out, and the choroidal thickness data of 9 regions of the fovea and the inner, middle and outer rings (upper, lower, nasal, and temporal) are obtained.

2. Follow-up Examinations:

- 1) Questionnaire: A questionnaire on adverse events following the intervention will be administered at each follow-up visit and unexpected visits for children in the intervention group. Children and their parents/guardians will be asked about the side effects, including but not limited to short-term glare, flash blindness, and afterimages.
- 2) Visual acuity: An ETDRS chart (Guangzhou Xieyi Weishikang, Guangzhou, China) with standard illumination will be used to measure distance visual acuity. Visual acuity measurement is performed at a distance of 4 meters. Uncorrected visual acuity will be measured for each follow-up visit, best corrected visual acuity will be measured for the baseline, 6-month and 12-month follow-up visit.
- 3) Ocular biometric measurements via IOLMaster: IOLMaster will be used to measure the axial length of both eyes. Five measurements will be taken for each eye. The axial length measurement will be based on the mean of these five values if the desired precision (<0.05 mm) is achieved.
- 4) Cycloplegia: Cycloplegia will be induced with three drops of 1% cyclopentolate administered at the 0, 5th, and 20th minute to each eye. The light reflex and pupil dilation will be checked after an additional 15 minutes. Dilation and light reflex status will be recorded and full cycloplegia will be justified if the pupil dilates to 6 mm or greater and the light reflex is absent.

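### Stopping a child for a serious eye event ends study participation, not just device use, so the remaining scheduled OCT and acuity checks can be lost

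*Combined protocol and SAP*

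**What the plan says.** The abstract's safety assessment names "Sudden vision loss" and "Structural damage to retina: tissue disruption or discontinuity, edema, or other abnormalities in the photosensory layer of the SS-OCT images".

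The withdrawal list in Section 3.1 opens with "A study investigator will terminate participation in the study for the following reasons". Two of its items matter here:

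- Item 2: "Patients continuously stop using Eyerising equipment for more than 14 days".
- Item 3: "Severe comorbidities or adverse events: patients cannot tolerate light, have obvious eye allergies such as tearing, skin rash", followed by an afterimage lasting more than 5 minutes.

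Neither vision loss nor retinal damage appears by name in that list. The follow-up safety list in Section 4.2 does not name them either; its nearest entries concern near acuity and blurred vision.

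The Section 4.3 schedule places distance vision at Visits 3 to 7, and OCT and slit-lamp examination at Visits 1, 5 and 7. For corrected acuity, Section 4.2 says "best corrected visual acuity will be measured for the baseline, 6-month and 12-month follow-up visit". Section 5.2 analyses safety in the ITT population and reports each adverse event individually.

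**The concern.** Finding these events is not the main difficulty. Vision and adverse events are checked at every follow-up visit, the adverse-event questionnaire also covers unplanned visits in the intervention group, and the fundus is examined at Visits 5 and 7. The difficulty is what happens next. The only action that the protocol attaches to a severe adverse event removes the child from the study. It has no separate step that stops the device and keeps the child under observation, and no rule for following an event until it resolves.

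The device is a Class 3R laser that children view twice daily, and safety is a stated purpose of the trial. Whether an acuity loss or an OCT lesion recovers once treatment stops is a central safety question, and the affected children are the ones who can answer it. Routine care may well examine them, but the plan does not say that those results are collected for the safety analysis.

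**Working it through.** The plan gives no figure on this point to reproduce. The check is a reading of the rules followed by a count from the schedule.

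**Reading the rules**

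1. The lead-in to the withdrawal list governs items 2 and 3, and what it ends is participation.
2. Item 3 applies at once. Item 2 applies after more than 14 days, if a safety stop is counted as non-use.
3. No visit after termination appears in Sections 3.1, 4.2, 4.3 or 5.2. Section 6 mentions a duration of surveillance that depends on serious adverse events, but this concerns site monitoring and sets no visit for a child.

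**Inputs for the count**

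- Follow-up visits 3, 4, 5, 6 and 7 at days 30, 90, 180, 270 and 365, each ±14 days (Sections 3 and 4.3).
- Follow-up OCT at Visits 5 and 7 (Section 4.3).
- Follow-up BCVA at 6 and 12 months, which are Visits 5 and 7 (Section 4.2).
- Assumptions: the visit at which participation ends is completed, and no examination follows it.

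**What is lost**

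Nominal days lost = 365 − day of the ending visit. The shortest loss takes Visit 7 at its earliest (day 351) and the ending visit at its latest. The longest takes Visit 7 at its latest (day 379) and the ending visit at its earliest.

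| Ended at | Visits lost | OCTs lost | BCVA tests lost | Days lost | Shortest | Longest |
|---|---|---|---|---|---|---|
| Visit 5 | 2 of 5 | 1 of 2 | 1 of 2 | 365 − 180 = 185 | 351 − 194 = 157 | 379 − 166 = 213 |
| Visit 4 | 3 of 5 | 2 of 2 | 2 of 2 | 365 − 90 = 275 | 351 − 104 = 247 | 379 − 76 = 303 |
| Visit 3 | 4 of 5 | 2 of 2 | 2 of 2 | 365 − 30 = 335 | 351 − 44 = 307 | 379 − 16 = 363 |

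**Does item 2 lose less than item 3?** No. If the device is stopped at the latest possible Visit 5 (day 194), the limit of more than 14 days is passed by day 194 + 15 = 209. The earliest Visit 6 is day 270 − 14 = 256. The same visits are lost. The same holds for a stop at Visit 4: 104 + 15 = 119, before the earliest Visit 5 at day 180 − 14 = 166.

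**Scale, under assumed rates only.** With 96 treated children and an assumed event risk of 0.5% to 3%, the expected number is 96 × 0.005 = 0.48 to 96 × 0.03 = 2.88. The chance of at least one event is 1 − 0.995^96 = 38% to 1 − 0.97^96 = 95%. These rates are illustrations, not figures from the documents. They show that any such cases would probably be few, so the outcome of each one matters.

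**The case against.** The strongest reply has three parts.

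**The device would be stopped anyway.** A reader might infer that the protocol gives no basis for stopping after vision loss or retinal damage. The documents do not support that. Item 3 opens with a general reference to severe adverse events under a mandatory lead-in, and its examples are milder than these two events. The device appendix says use should follow the instructions, which list fundus retinopathy as a contraindication and advise stopping for eye disease or discomfort. An ophthalmologist at each of the six centres also reads the OCT scans for structural anomalies. This part stands. What is missing is an explicit trigger, and that is secondary.

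**Loss of follow-up is inferred from silence.** Section 3.1 does not say that visits cease. Section 5.2 includes children with at least one follow-up visit whatever their adherence to treatment or visits, and analyses safety in the ITT population. The flow chart and consent pages are not visible and might address the matter. This softens the point, so the claim is that checks can be lost, not that they will be. But an analysis population schedules no examination, and the same paragraph of Section 5.2 censors children who discontinue treatment.

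**Other parts of the text might be drawn in.** The Section 4.2 heading "Optical coherence tomography (optional): SS-OCT fundus image acquisition and data processing" might suggest that OCT need not be done, yet the visit lists and the schedule include it at Visits 1, 5 and 7, so this is a labelling inconsistency. Item 4, on repeated serious safety problems, might be read as another individual rule, but it stands beside regulator and sponsor suspension and may apply to the whole trial. One might also count the 185 × 2 = 370 sessions scheduled between Visits 5 and 7 as exposure at risk, but they describe a child who continues, not one who has been stopped.

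**Conclusion.** The point holds in this form: items 2 and 3 end participation where ending device use would be enough, and the visible text provides no safety follow-up afterwards. A child stopped for vision loss or retinal damage can lose between 2 and 4 of the 5 follow-up visits, and one or both of the follow-up OCT and BCVA tests, depending on whether participation ends at Visit 5, 4 or 3.

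This rests on termination meaning that no further study examinations take place, which is the natural reading of the rule but is not spelled out. It does not show that affected children would stay on the device or that events would go unnoticed. The weakness is in the completeness of safety outcomes, and the change is worth making because it costs little.

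**What to change.** 1. Reword items 2 and 3 of the withdrawal list so that a stop for safety reasons ends device use only. If the family agrees, the child stays in the already scheduled visits through Visit 7.
2. State in Section 5.2 that results collected after a safety stop enter the ITT safety analysis. How efficacy data after a stop are handled is a separate question and is left unchanged.
3. Leave item 4 as it stands, since it may be a trial-level rule.
4. For clarity, list sudden vision loss and structural retinal damage on OCT under item 3 as examples for which a single occurrence suffices, and add both to the follow-up safety list in Section 4.2.

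The cost is a short amendment, plus visits for a few children who would otherwise have left the study. No visit or scan is added beyond the schedule. One limit follows from that: a child stopped at Visit 4 would still wait until Visit 5, nominally 180 − 90 = 90 days, for the next scheduled OCT and BCVA test, unless the site examines the child sooner.

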3.4 Intervention

1. Intervention group: Use the Eyerising RLRL device to treat with the treatment device twice a day, three minutes each time, with an interval of 4 hours. The method of use is as follows:

- A. Put the instrument on a stable desktop, confirm the interface before connecting accessories;
- B. Connect the power supply and turn on the power switch;
- C. Let the user sit in a suitable position, loosen the hand-wheel on the side of the treatment device, and adjust it up and down to the most suitable angle to make the eyes relatively comfortable when resting on the goggles, and fix the hand-wheel to a fixed angle;
- D. Enter the subject's unique account and password, and click Confirm to log in;
- E. After logging in, the first interface enters the photo-kinetic energy treatment item by default, take off the glasses, click OK. Then, making sure that there is visible red light in the eye position corresponding to the instrument, and put the eyes close to the blue eye mask;
- F. For the first use, please place your hands on the top of the treatment device and adjust the interpupillary wheel on the top at the same time. It is better to regard the two light points as one light point. If not, the brightest light also can be used.
- G. After three minutes of use, the light kinetic energy will automatically stop, leave the blue eye mask, close your eyes and rest for 3-5 minutes, until the front and back image spots disappear;

H. After using the instrument, turn it off.

2. Control group: single vision spectacle lenses

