- 5) Cycloplegic auto-refraction: Cycloplegic auto-refraction will be conducted using an auto-refractor (KR-8800, Topcon, Tokyo, Japan). The same auto-refractor will be used throughout the study. It will be calibrated before each examination session to ensure there is no equipment drift during the long follow-up process.
- 6) Slit-lamp examination: Slit-lamp examination will be used to examine the anterior segment, lens, vitreous, and fundus, and any abnormalities will be recorded.

7) Optical coherence tomography (optional): Swept Source-OCT (DRI OCT-1 Atlantis, Topcon) will be used to capture the macular scan. Shooting mode: 12 mm radial scan mode (follow up mode).

8) Safety assessment

- ① The incidence of allergic reactions;
- ② Afterimage duration exceeds 5 minutes;
- ③ Decreased near visual acuity;
- ④ Levels of side effects such as photophobia and blurred vision;
- ⑤ Increased intraocular pressure, headache, nausea and vomiting, etc.

Follow-up Schedule

(1) Visit 1: Screening period (-7~0 days)

- 1) Sign the "Informed Consent";
- 2) Record the general information of the patient;
- 3) Record the medical history;
- 4) Perform visual inspection, axial inspection, intraocular pressure inspection, equivalent spherical lens measurement, slit lamp inspection, OCT inspection;
- 5) Review the inclusion and exclusion criteria;
- 6) Record the combined/concomitant medication;

(2) Visit 2: Enrolment and randomization (day 0)

- 1) Randomly group, and the intervention group will receive experimental devices;
- 2) Record device defects;
- 3) Record the combined/concomitant medication;

(3) Visit 3: Day 30±14

- 1) Perform visual inspection, axial inspection, and intraocular pressure inspection;
- 2) Record the combined/concomitant medication;
- 3) Record adverse events/device defects.

(4) Visit 4: Day 90±14

- 1) Perform visual inspection, axial inspection, and intraocular pressure inspection;

2) Record the combined/concomitant medication;

3) Record adverse events/device defects.

(5) Visit 5: Day 180±14

1) Perform vision examination, axial examination, intraocular pressure examination, equivalent spherical lens, slit lamp examination, and OCT;

2) Record the combined/concomitant medication;

3) Record adverse events/device defects.

(6) Visit 6: Day 270±14

1) Perform visual inspection, axial inspection, and intraocular pressure inspection;

2) Record the combined/concomitant medication;

3) Record adverse events/device defects.

(7) Visit 7: Day 365±14

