Monitoring begins immediately after initiation. The first case from each participating center is enrolled, followed by monitoring at 30% and 50% of enrollment, and finally after completion of enrollment. The duration of surveillance is determined by the occurrence of serious adverse events. If there are abnormal enrollment situations or a high frequency of program violations, the frequency of monitoring will be increased accordingly. The monitoring focuses on subjects, investigators, and equipment used, primarily assessing the following aspects:

1. Informed consent status: Ensuring that the number of signed informed consent forms matches the number of cases in the clinical trial report (including cases of screening failure), verifying that the version of the signed informed consent form aligns with the version approved by the ethics review, confirming that the ethics review was conducted prior to the signing of the informed consent form, assessing the completeness and standardization of the informed consent form (including inclusion of the clinical trial personnel's contact information, signing date, etc.), and verifying that the subject's signed informed consent form was signed by the subject or their legal representative (if necessary, confirming the actual participation of subjects in the trial).
2. Implementation assessment: Whether the clinical trial procedures adhere to the clinical trial protocol, including the subject selection and exclusion criteria, sample size, selection of control devices, trial duration, observation endpoints, and the management and documentation of adverse events; verifying that the original data collection and case report forms are signed by the clinical trial personnel.
3. Equipment assessment: Whether the delivered equipment product has a valid product inspection report issued by a qualified testing agency, and whether the management record of the tested product (including transportation, reception, processing, storage, distribution, recycling, and disposal) is complete; verifying if the quantity is consistent; assessing if the transportation conditions, storage temperature, storage conditions, storage duration, and safety validity period of the tested product meet the requirements; confirming if the tested product matches the product name, specification, and model

stated in the test report and clinical practice report. After each inspection, the inspector will generate an inspection report based on the findings.

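### The 5-minute after-image limit is assessed at visits and ends participation under 3.1, but neither 3.4 step G nor 4.2 gives a stop-and-report instruction that would bring that rule into play between visits

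*Combined protocol and SAP*

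**What the plan says.** **Stopping rule.** Section 3.1, under participant withdrawal or termination, opens with "A study investigator will terminate participation in the study for the following reasons". Item 3, on severe comorbidities or adverse events, includes that "the after-image time after low-energy laser treatment exceeds 5 minutes".

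**Session instruction.** Section 3.4 prescribes treatment "twice a day, three minutes each time, with an interval of 4 hours". After each session, step G tells the user to "close your eyes and rest for 3-5 minutes, until the front and back image spots disappear". Step H is to switch the device off.

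**Follow-up checks.** In section 4.2, item 8 of the follow-up examinations names an after-image longer than 5 minutes as a safety item, as the abstract also does. Adverse events are recorded at Visits 3 to 7. Item 1 of the same list is an adverse-event questionnaire "administered at each follow-up visit and unexpected visits for children in the intervention group", covering side effects "including but not limited to short-term glare, flash blindness, and afterimages".

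**Device hand-over.** Under Visit 2 (day 0), section 4.2 has: "Randomly group, and the intervention group will receive experimental devices".

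**General safeguards.** The device precautions tell users to stop, or follow the doctor's advice, if they feel discomfort. They also classify the device as a Class 3R laser product. Section 6, item 1, lists "contact information, signing date, etc" among the consent-form contents that monitors check. Section 8 lets families ask questions while the study is running.

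**The concern.** The child, or a parent nearby, is the first to know that an after-image has passed 5 minutes. The visible instruction to that person treats after-images as expected and asks only for patience. A family that follows step G exactly can wait out a longer after-image and start the next session about 4 hours later, without knowing that the protocol counts this as a reason to end participation.

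What is at stake depends on the pattern. If over-limit after-images recur, the main issue is continued twice-daily exposure after the plan's own stopping criterion has been met. If the event is isolated, the main issue is measurement: its duration has to be recalled weeks or months later at a visit, so the reported count of over-limit events could be wrong in either direction.

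A second, smaller gap is that 3.1 does not say whether a single over-limit session is enough to end participation.

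**Working it through.** **1. The provisions side by side**

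| Place | Names the 5-minute limit? | Says what to do when it is exceeded? | When it operates |
|---|---|---|---|
| 3.1, item 3 | Yes | Yes: the investigator ends participation | Once the investigator knows |
| 3.4 step G | Only as the upper end of a 3-5 minute rest | No | Every session |
| 4.2 item 8 | Yes | No; 3.1 supplies the action | Follow-up visits |
| 4.2 item 1, questionnaire | After-images named, no duration in the description | No | Scheduled and unexpected visits |
| Device precautions, item 4 | No | Stop, or follow medical advice, on discomfort | Any time |

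The plan therefore has a threshold, an assessment at visits and an action. It lacks a step that carries the observation from the session to the investigator between visits. The text does not say what prompts an unexpected visit, and a painless after-image need not be felt as discomfort.

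**2. Time and sessions between scheduled checks**

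Inputs: visits at days 30, 90, 180, 270 and 365, each ±14 days (section 3); device handed out at day 0 (4.2); 2 sessions a day (3.4).

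Nominal gap = later visit day − earlier visit day. Shortest gap = (later − 14) − (earlier + 14). Longest gap = (later + 14) − (earlier − 14). Day 0 has no window. Sessions = 2 × days.

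| Interval | Nominal days | Nominal sessions | Range of days with windows | Sessions at longest gap |
|---|---|---|---|---|
| 0 to 30 | 30 | 60 | 16-44 | 88 |
| 30 to 90 | 60 | 120 | 32-88 | 176 |
| 90 to 180 | 90 | 180 | 62-118 | 236 |
| 180 to 270 | 90 | 180 | 62-118 | 236 |
| 270 to 365 | 95 | 190 | 67-123 | 246 |

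The nominal sessions sum to 730 (2 × 365). The longest gap is 379 − 256 = 123 days, or 246 sessions. The documents give no event rate, onset time, adherence or rate of spontaneous reporting, so nothing here can be turned into a likelihood of harm.

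**3. What acting on the rule promptly could cost the primary analysis**

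The plan's own figure first. With a difference of 0.20 mm, SD 0.40 mm (standardised 0.5), α 0.05 taken as two-sided and 90% power, the two-sample t test needs 85.03, so 86 per group and 172 in total. Then 172 / 0.9 = 191.1, rounded up to 192. Section 3.6 is reproduced.

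Now assume 1, 5 or 10 intervention-arm children are lost beyond the planned 10%:

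| Intervention v control | Power |
|---|---|
| 86 v 86 | 90.3% |
| 85 v 86 | 90.2% |
| 81 v 86 | 89.4% |
| 76 v 86 | 88.4% |

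The 1-10 range is an assumption. The planned analysis is a longitudinal mixed model, so the t test is only a guide to the size of the loss.

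For one child, suppose the event would have been recognised at the next visit anyway, with axial length measured there before termination. Stopping at once then loses 1 of the 5 follow-up axial-length visits. If the event would never have been recognised, stopping loses 1 to 5.

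**The case against.** The strongest reply is that most of the machinery is already there. Section 4.2 names the exact threshold as a follow-up safety item, adverse events are recorded at every follow-up visit, and 3.1 states the action. All of that stands. A reader might infer that the plan keeps no record of over-limit after-images, or never asks about their duration. The documents do not support that: item 8 sits in the same follow-up list as the questionnaire, so asking about durations over 5 minutes is already specified.

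A second reply is that step G is one line of operating instructions, and that instructions to stop or call usually sit in family material. The consent pages were removed before review, the questionnaire form is not in the documents, and the device section refers to a manual. The device has individual logins and a network connection, and the appendix title mentions a data management system that the visible text does not describe. What is captured between visits therefore cannot be judged. This also stands, and it limits the point to the visible text. Families probably do have a contact route. What is not visible is the trigger for using it.

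Third, home use is not stated. It is inferred from devices being handed out at day 0 and used twice daily while visits are weeks to months apart. The device precautions also provide for shared use in a hospital or clinic.

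Finally, the session counts might be read as a measure of injury or as exposure that will occur. They are neither. The nominal 60 to 190 are not upper limits either, because the windows allow up to 246.

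**Conclusion.** The point holds in a narrow form. The plan defines an over-limit after-image, assesses it at visits and says what the investigator does about it. The instruction used at each session does not tell the family to stop and report, and 4.2 does not supply that instruction either. A child can comply fully with step G and continue treatment after meeting a termination criterion, for up to one inter-visit interval if the event is then picked up: nominally 30 to 95 days, at most 123.

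This rests on three assumptions: that sessions take place away from the clinic, that no unexpected visit or spontaneous call intervenes, and that unseen family material does not already give the instruction. It is a matter for consideration, not a flaw in the efficacy design. The case for acting is that the change is cheap and applies a criterion the plan already has.

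**What to change.** **Section 3.4, step G.** Reword along these lines: rest until the spots disappear; if any are still visible at 5 minutes, write down the date and the time they took to disappear, have no further session, and contact the site the same day.

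**Section 3.1.** Add that the site promptly confirms the event and applies the existing criterion, and state whether one confirmed session is enough.

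**Section 4.2.** No new assessment is needed. Check that the questionnaire form carries the item 8 threshold, and report the number of children and events from both family reports and visits.

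If the family sheet already gives this instruction, a reference to it in step G is sufficient.

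**Cost.** One sentence and one phrase, a small reporting burden, some extra calls and a few missed sessions. A few affected children may be discontinued earlier. Under 5.2 they are censored, and this happens in the intervention arm only. A child stopped before the day-30 visit may have no follow-up visit and so drop out of the analysis. Measuring axial length when the site confirms the event would limit that loss. On the assumed 1 to 10 additional losses, power stays between 90.2% and 88.4%.
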